11.2 Patient Enrollment Log

A Patient Enrollment Log shall be maintained throughout the study and is included in the Investigator Binder. All patients who are screened and offered study participation and/or are participating in the inclusion/exclusion process and/or are consented for the study shall be entered in the log regardless of study eligibility. Finally subjects enrolled in the study must be sequentially entered in the log as well.

11.3 Determination of Eligibility

Patient eligibility for enrollment will be determined for consenting candidates based upon the inclusion/ exclusion criteria. Patients must meet all of the inclusion criteria and none of the exclusion criteria in order to be offered enrollment into the study. Determination of eligibility may include an interview to assess significant patient medical/ surgical history, history of present illness/ injury, evaluation of present pain and functional capacity, and a radiographic assessment. Eligible patients will be offered enrollment into the study. For the purposes of this clinical study, patients will be considered subjects after enrollment has been completed.

11.4 Informed Consent

All patients must sign a written Informed Consent (Appendix C) approved by the Ethics Committee (EC), prior to participate in the inclusion/ exclusion criteria screening process

and thus prior to be enrolled in the clinical study. This signed document is required for patients to be enrolled in the study and to receive the devices as defined by this protocol and will further serve as documentation of an offer to participate in the study for those patients who elect not to do so. No patient will be enrolled without having signed the Informed Consent.

11.5 Baseline/Pre-operative Assessment

Data required for completion of the pain, functional and quality-of-life evaluations as well as the radiographic evaluations will be collected preoperatively. All subject data will be used in the analysis of overall pain and functional performance, survivorship, and radiographic parameters and will include the following Case Report Forms (CRF):

1. Inclusion / Exclusion Criteria Form
2. Demographic Evaluation Form
3. Physical Exam Form
4. Oxford Hip Score Form
5. Patient Activity Questionnaire Form
6. Harris Hip Form
7. Concomitant Medication Record
8. Radiographs Evaluation Form (standing anteroposterior (AP) and standard lateral views of the operative hip)
9. EQ-5D Form

11.6 Surgical Technique

The surgical technique for the *Allofit* IT Acetabular System (Doc. No. 06.01651.012) is provided in the Investigator Binder.

11.7 Surgery until Discharge Assessment

Post-operative management for study subjects will follow the standard-of-care for patients undergoing total hip arthroplasty. Required surgical and discharge data will include, but is not limited to the following:

1. Operative Information Form
2. Immediate Post-op Evaluation Form
3. Radiographs Evaluation Form (supine anteroposterior (AP) view of the operative hip)
4. Adverse Events
5. Protocol Deviations

11.8 Follow-up Procedures (Data Collection)

Data required for completion of the pain, functional and quality-of-life evaluations as well as the radiographic evaluations will be collected postoperatively at 6 months (\pm 1 month), 1 year (\pm 2 months), 2 year (\pm 2 months), 3 year (\pm 2 months), 5 year (\pm 2 months), 7 year (\pm 2 months), and 10 year (\pm 2 months). Post-discharge data collection will include, but is not limited to the following:

1. Physical Exam Form
2. Oxford Hip Score Form
3. Patient Activity Questionnaire Form
4. Harris Hip Form
5. Concomitant Medication Record
6. Radiographs Evaluation Form (standing anteroposterior (AP) and standard lateral views of the operative hip)
7. EQ-5D Form
8. Adverse Event Form (if any)
9. Protocol Deviation Form (if any)
10. Explanted Device Form (if any)
11. Study Completion Form (if the case)

Patient follow-up is expected to continue through 10 years of follow-up for each case although it is expected that a few subjects may succumb to other medical problems or otherwise lost to follow-up prior to completion of the 10 years of follow-up. All subject data will be used in the analysis of overall pain and functional performance, survivorship, and radiographic parameters. Data will continue to be collected until the subject completes the study, is lost to follow-up, one or several devices are removed due to revision, or the study is otherwise closed.

11.9 Minimization of Subjects Lost to Follow-up

Subject follow-up is extremely important for the conduct of a clinical study. The expectation is to maintain the highest rate of follow-up compliance possible throughout this study. In an effort to minimize *lost to follow-up* study subjects, the following recommendations and/or study requirements are essential to ensure proper patient selection and compliance:

1. Patient Eligibility: Subjects will be selected according to patient eligibility criteria detailed in Section 8 and are expected to return for all follow-up visits.

2. Patients counseled: Patients will be counseled during the informed consent process on the importance of returning for follow-up visits.
3. Patient Exclusion: Patients who are not willing to return for study required follow-up visits and/or are not willing to comply with the follow-up schedule will not be considered for enrollment in the study.
4. Subject Due Listings: In addition to proper patient selection, Zimmer will provide subject due notices to the sites on a regular basis in order to track each study participant and monitor adherence to the required follow-up visit timeframes. The subject due listings will facilitate scheduling the subjects for their return office visits.
5. Financial Hardship: If during the course of the study it is determined that a subject is experiencing a financial hardship that prevents the subject from returning for follow-up visits, Zimmer should be notified to discuss possible financial assistance which may be available to the subject.
6. Contact Tracking: Attempts to contact subjects will be documented. It is recommended that the first three attempts be made by telephone.

Recommended Contact Attempts

If	then
A response is not received from the three phone calls	The Investigator should send a letter to the subject explaining the follow-up agreement per the informed consent.
A response is not received from the Investigator's letter	The Investigator should send a certified letter to the subject.
A response is not received from the Investigator's certified letter	The Investigator should use any additional contacts provided by the subject to contact the subject.
If all attempts to contact the subject are unsuccessful or the subject is contacted and chooses to withdraw from the study	The Study Completion CRF will be completed and will specify the reason the subject is no longer participating in this study.

11.10 Radiographic Definitions and Methods

All radiographic evaluations performed according to the protocol will be reviewed by the Investigator at the time of the evaluation for assessment of post-operative adverse events as well as for standard patient management purposes. If a radiographic adverse event is identified by the Investigator during the course of the investigation, the Investigator must document the event and report the radiographic findings on Adverse Event Report CRF for Sponsor review. In addition, assessments of radiographic films for evidence of

radiolucencies, osteolysis, subsidence, acetabular cup migration, and change in acetabular cup angle, will be performed.

11.10.1 Required Radiographic Views

Standing anteroposterior (AP) and standard lateral radiographs of the operative hip are required to be captured before surgery and at 6 months, 1, 2, 3, 5, 7, and 10 years post-operatively. At the immediate post-operative interval, only a supine AP view of the operative hip is required.

Every effort should be made to obtain all radiographic views for every interval at the same institution to maintain consistency. However, if radiographs are completed at a different institution within the required interval and copies or originals are available, they may be used for study submission provided they meet the required specifications.

11.11 Reporting of Adverse Events and Adverse Device Effects

Adverse Events and Adverse Device Effects have to be documented during the whole course of the study (for details see Section 14).

12 Implant Information

12.1 Description of the Device

A. Investigational Devices

1. *Allofit®* IT Acetabular Shell
2. *Longevity®* Liner

B. Investigational Device Description

1. *Allofit* IT Acetabular Shell

The shells are mainly made from Titanium (Protasul®-Ti Alloy). The shells are available with or without screw holes. The Allofit IT Shells have no screw holes, the Allofit-S IT Shells allow for the use of screws to provide additional fixation and security, particularly in those cases where acetabular bone stock is deficient. Only 6.5 mm diameter *Allofit* Screws (Catalog numbers 4301-07-xxx) and 6.5 mm diameter *Trilogy®* screws (Catalog numbers 00-6250-065-xx) should be used with the *Allofit-S* IT Acetabular Shell. Screw holes that are not utilized for fixation and the dome hole may be closed with optional plugs.

The *Allofit* IT Acetabular Shell is packaged without a liner. The selection of an appropriate liner is required to complete the acetabular component.

2. *Longevity* Liner

The Longevity Liners are made from long Polyethylene chains (CH₂)_n which are cross-linked by E-beam irradiation. The Longevity Liners are secured in the shell by a snap feature. Anti-rotation tabs provide rotational stability. The inner diameter of the liner must match outer diameter of the selected femoral head.

C. Intended use / Surgical Technique

Total Hip arthroplasty is intended to reduce pain and increase hip mobility. A system consisting of a stem, a femoral head and a cup (= shell + liner) is used for the treatment of degenerative diseases or trauma of the hip. The articulation is comprised of a femoral head and a corresponding liner. All components are intended for single use only.

The surgical technique for the *Allofit* IT Acetabular System (Doc. No. 06.01651.012) can be found in the Investigator Binder.

12.2 Risks

The risks associated with the use of the *Allofit* IT Acetabular System are similar to those with the use of other standard acetabular hip systems when used for the same clinical indication. These risks are categorized as those anticipated to be related to general surgical risks, total hip arthroplasty risks, or those potential risks associated with the investigational system. Unanticipated adverse events may occur as well.

13 Statistical Considerations/ Evaluation

13.1 Analysis Objectives

The assessment of efficacy for subjects receiving the total hip replacement system will be determined using the overall pain score and functional performance. Clinical success will be defined as a modified Harris Hip score of > 80 that included a rating of 'mild', or 'no pain'; a failure will be defined as a modified Harris Hip score < 80. Any study hip that required a subsequent surgical intervention where a stem head, cup, or liner was removed, or where a removal was planned, was considered a failure regardless of the Harris Hip score. Success rates will be expressed as percentages and primary summary results will be presented in tables which will contain the number and percentage of patients classified as a clinical success for the treatment group.

The assessment of safety will be evaluated by monitoring the frequency and incidence of adverse device effects in investigational subjects. As part of the safety profile, a survival analysis will be done.

The endpoints that contributed to the composite success will be summarized separately, that is, the Harris Hip Scores, both function and pain. Additionally, there are measures of interest which will be used to assess the investigational device such as radiographic success, all components included in the assessment of radiologic success, the Oxford Hip Score patient satisfaction scores, patient activity scores, concomitant medication usage, and incidence of adverse events.

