
6. Health State: To help people say how good or bad a health state is, we have drawn a scale at the right (rather like a thermometer) on which the best state you can imagine is marked 100 and the worst state you can imagine is marked by 0. Please mark through the line at the place which indicates how good or bad your health state is today.
		
 Office Use Only   . 		

31-AUG-2010

Initials of Person Completing Form:

60363

Allofit IT Bearing System

Harris Hip

PLEASE COMPLETE ONE FORM PER OPERATIVE SIDE

Form 9

FOR ZIMMER USE ONLY

Patient Initials

Case ID

Date of Surgery - -
(DD-MM-YYYY)

Investigator ID

Operative Side Left
 RightVisit Date - - Examination Period: Preop 6 Month 1 Year 2 Year 3 Year 5 Year 7 Year 10 Year

1. Evaluation of pain: (check one box only)

- None Moderate
 Slight Marked
 Mild Disabled

2. Evaluation of function:

A. Daily Activities (check one box in each subsection):

1. Stairs:
 - Normally without use of banister/railing
 - Normally using banister/railing
 - Using any method
 - Unable to do stairs
2. Transportation
 - Able to enter public transportation
 - Unable to enter public transportation
3. Sitting:
 - Comfortable in any chair for one hour
 - Comfortably on a high chair for one-half hour
 - Unable to sit comfortably in any chair
4. Socks and Shoes:
 - Puts on socks and shoes with ease
 - Puts on socks and shoes with difficulty
 - Unable to put on socks and shoes

B. Gait (Check one box in each subsection):

1. Limp
 - None
 - Slight - detected by trained observer
 - Moderate - detected by patient
 - Severe - markedly slows or alters gait

2. Support

- None
 Single cane for long walks
 Single cane most of the time
 One crutch
 Two canes
 Two crutches (walker)
 Unable to walk even with support

3. Distance walked

- Unlimited
 Six blocks (> 500 m, 31-60 min)
 Two or three blocks (< 500 m, 2-30 min)
 Indoors only
 Bed and chair

3. Absence of deformity:
(check one box in each subsection)

- A. $\geq 30^\circ$ fixed flexion contracture:
 - Absence Presence
- B. $\geq 10^\circ$ fixed adduction:
 - Absence Presence
- C. $\geq 10^\circ$ fixed internal rotation in extension:
 - Absence Presence
- D. Limb-length discrepancy > 3.2 cm:
 - Absence Presence

4. Range of Motion:

- A. Flexion: °
- B. Abduction (In Flexion) °
- C. Adduction (In Flexion) °
- D. External Rotation (In Extension) °

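### The clinical-success rule in section 13.1 does not say how the Slight pain box on Form 9 or a score of exactly 80 is classified (minor)

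*Combined protocol and SAP*

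**What the plan says.** Section 13.1 (Analysis Objectives) sets the success rule: "Clinical success will be defined as a modified Harris Hip score of > 80 that included a rating of 'mild', or 'no pain". It continues that "a failure will be defined as a modified Harris Hip score < 80". A further sentence covers removals: a hip where "a stem head, cup, or liner was removed, or where a removal was planned, was considered a failure regardless of the Harris Hip score". The primary summary tables are to show "the number and percentage of patients classified as a clinical success for the treatment group". The same section adds that "The endpoints that contributed to the composite success will be summarized separately", naming the Harris Hip function and pain results.

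The pain rating comes from Form 9 in Appendix B. The item is headed "Evaluation of pain: (check one box only" and has two columns of three boxes. Its first row pairs None with Moderate. The next two rows read "Slight Marked" and "Mild Disabled". Down the columns the order is None, Slight, Mild, Moderate, Marked, Disabled. The form prints no point values.

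No section maps Slight to a qualifying rating, says that ratings better than Mild qualify, or assigns hips that meet neither definition.

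**The concern.** The rule names two pain ratings, but the form that feeds it has six. Slight and Mild cannot both be ticked for one hip at one visit, so a program written from the words of 13.1 would count a hip above 80 rated Mild and leave out the same hip rated Slight. By box order Slight is the milder rating, so that result is unlikely to be intended.

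The two score conditions also leave out a score of exactly 80, and the failure sentence has no pain condition. The plan does not say whether a hip in neither class stays in the denominator. Two analysts could follow 13.1 faithfully and report different success percentages from the same data. In an uncontrolled study analysed by the sponsor or its designee, that choice is better made before the data are seen.

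**Working it through.** There is no stated figure to reproduce. The check is to apply the rule to every combination of score and pain box.

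**Inputs.** The success, failure and removal sentences come from 13.1, and the six pain boxes from Form 9. 'No pain' is taken as the box None. That mapping is natural, but it is also not written down.

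**Hips with a removal done or planned.** These are failures in every cell, so this group has no gap.

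**Hips with no removal done or planned.**

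| Form 9 pain box | Below 80 | Exactly 80 | Above 80, literal | Above 80, mild or better |
|---|---|---|---|---|
| None | failure | neither | success | success |
| Slight | failure | neither | neither | success |
| Mild | failure | neither | success | success |
| Moderate, Marked, Disabled | failure | neither | neither | neither |

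Three score bands times six boxes give 18 cells.

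- Literal reading: 2 success, 6 failure, 10 in neither class (6 at exactly 80 and 4 above 80).
- Mild or better: 3 success, 6 failure, 9 in neither class (6 at exactly 80 and 3 above 80).

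The choice of reading moves one cell, Slight above 80. Cell counts show that the rule is incomplete. They do not show how many hips are affected.

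**Effect of Slight on the percentage.** Let a be the share of hips above 80, unrevised and rated None or Mild. Let s be the share above 80, unrevised and rated Slight, and f the share that fail. Suppose first that no other hip is unclassified, so a + s + f = 1.

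- Mild or better: rate = a + s, so nothing is lost.
- Literal, Slight hips kept in the denominator: rate = a, a loss of s.
- Literal, Slight hips dropped: rate = a/(1 − s), a loss of (a + s) − a/(1 − s) = s·f/(1 − s). This cannot exceed s, because f is at most 1 − s.

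The loss therefore lies between 0 and s. The documents give neither s nor f. As an illustration on assumed values only, s = 10% and f = 15% (so a = 75%) give 85.0% under mild or better, 75.0% under the literal rule with Slight kept, and 0.75/0.90 = 83.3% with Slight dropped. With s = 0 all three agree.

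**Effect of the other unclassified hips.** Let u be their share (exactly 80, or above 80 with a worse pain rating). Dropping them raises the percentage. With assumed a = 75%, s = 5%, u = 5% and f = 15%, counting Slight as success and the u hips as failures gives 80.0%. The literal rule with all unclassified hips dropped gives 0.75/0.90 = 83.3%. That rise comes from the denominator: with the u hips dropped in both cases, counting Slight gives 0.80/0.95 = 84.2%, so Slight alone still lowers the rate.

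**Revised hips at later visits.** Section 11.8 ends data collection once a device is removed at revision, and Form 15 then asks for the Study Completion form. A revised hip has no later Form 9. If r is the share of such hips and they fall out of the denominator, the rate is divided by 1 − r and so rises. Any repair of the rule must keep them in.

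**Unit.** The removal sentence in 13.1 speaks of hips and the table sentence of patients. Sections 10.1 and 10.3 give bilateral patients two sets of forms and two case IDs, so the two percentages can differ.

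**The case against.** The strongest reply is that 13.1 paraphrases the form. It writes 'no pain' where the form prints None, so it is not quoting box labels. A phrase that names an upper limit and the absence of pain is naturally read as a range. The literal reading ranks Mild above Slight, which is itself a reason to reject it. On the range reading the Slight gap disappears and the loss is zero. This stands as a plausible reading, and it is why the lower end of the effect is zero. It does not settle the matter, because the text never states it, and it leaves exactly 80 unassigned.

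The second reply is that little depends on this rate. It is descriptive, with no test. Section 9.1 lists the Harris Hip Score for pain and function, without this success rate. The sample size in 13.3 rests on 10-year survival. Pain and function are also reported separately, and Form 9 keeps every box, so the rate can be recomputed under either reading. All of this stands and fixes the grade as minor. One limit remains: if pain is tabulated by category under 13.2, the Slight total is visible but is not crossed with a score above 80. It gives only an upper bound on the hips affected.

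A reader might go further and infer that the plan excludes Slight hips, so that its main efficacy result will be understated by a known number of points. The documents do not support that. They do not fix the literal reading, they give no distribution of pain ratings, and 13.1 uses the word primary for summary tables without naming a primary endpoint. Nor does the count of 10 unclassified cells mean that most hips are unclassified. Six of those cells are a single score value, and the documents do not show whether the three with worse pain above 80 can occur.

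**Conclusion.** The point holds as a minor defect of definition. Success and failure in 13.1 are not exhaustive against the trial's own form: Slight above 80 is unassigned on a literal reading, and exactly 80 is unassigned on either reading. The effect of Slight runs from zero, if mild or better was meant, to s, if the rule is coded literally and unclassified hips stay in the denominator. The size of s cannot be obtained from the documents.

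The conclusion assumes that 'no pain' means the box None and that the printed box order is the order of severity. The second assumption bears only on why the literal result looks unintended. The gap itself does not depend on it.

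**What to change.** Replace the success and failure sentence in 13.1, leaving the removal sentence as it is, with wording such as:

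*At each visit a hip is a clinical success if its Harris Hip score is above 80, its Form 9 pain rating is None, Slight or Mild, and no removal covered by the next sentence has been done or planned. Every other hip in the denominator is a failure. The denominator is every hip with a Form 9 score at that visit, plus every hip with a removal done or planned at or before that visit, whether or not it is still followed.*

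The sponsor should confirm four things:

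- **Slight** counts as a qualifying rating.
- **Exactly 80, and above 80 with a worse pain rating,** have the class intended. As drafted both are failures, giving 3 success and 15 failure cells. If exactly 80 with a qualifying rating is to be a success, the split is 6 and 12. Either version is exhaustive.
- **Unit:** whether the percentage is per hip, as drafted, or per patient, and if per patient how bilateral cases are combined.
- **'Modified':** the draft omits the word. Keep it only if the Form 9 items that make up the score are stated.

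The cost is a short edit to 13.1 and a small change to the analysis code. No new data are needed, because Form 9 already records every pain box. The reported rate may shift slightly from what the present wording would have produced.

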The subject of this clinical investigation is the *Allofit* IT Shell in combination with the *Longevity* Liners in primary total hip arthroplasty. This system consists of a cementless modular Acetabular Shell, a modular liner, and a modular femoral head. The characteristics of this THA system may allow for reduction in wear and osteolysis as compared to other approved and marketed THA systems and thus increase the expected implant life.

6 Study Objectives

The objective of this study is to obtain survival and outcome data on the *Allofit* IT Shell in combination with *Longevity* Liners in primary total hip arthroplasty. This will be done by analysis of standard scoring systems, radiographs and adverse event records. Data will be used to monitor pain, mobility and survivorship, and to confirm the safety and efficacy of the *Allofit* IT with HXPE in primary total hip arthroplasty.

a) Safety:

Will be evaluated by monitoring the frequency and incidence of adverse events (AE), serious adverse events (SAE), adverse device effects (ADE) and serious adverse device effects (SADE)

b) Efficacy:

Will be determined by comparing the overall pain and functional performances (based on the Harris Hip Scoring system), survivorship, subject quality-of-life and radiographic parameters (radiolucencies, osteolysis, subsidence, cup migration, change in cup angle and change in femoral shaft angle) of study subjects who received the *Allofit* IT Acetabular System

a. Pain and Functional Performance:

Measurements will be based on the Harris Hip Scoring (HHS) System [39]

b. Subject Quality-of-Life:

Will be determined by the Oxford Hip Score [42] and the EQ-5D [41]

c. Radiographic parameters:

X-rays will be evaluated for radiolucencies, cup migration, osteolysis, subsidence, and change in cup angle

d. Survivorship:

Based on removal or intended removal of the device and will be determined using the Kaplan-Meier method

The data will meet Zimmer's obligation to collect device vigilance and post market surveillance information for European regulatory bodies.

7 Study Design

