7.2 Study Duration

After the initial visit followed by the surgery, the patient is expected to participate in the study for a time period of 10 years. Cases will be recruited during a period of 24 months, and the study will last until complete collection of the 10 years follow-up data.

8 Study Population

The study population will be comprised of 200 males and females who require primary total hip arthroplasty. Subjects will be enrolled at 5 investigative centers. Subjects must be geographically accessible throughout the study and be willing and able to attend required follow-up appointments. Candidates who express interest in study participation will be offered informed consent, and eligibility will be determined based upon the inclusion/exclusion criteria.

A. Inclusion Criteria

- Patient is 18 to 75 years of age, inclusive.
- Patient is skeletally mature.
- Patient qualifies for primary unilateral or bilateral total hip arthroplasty (THA) based on physical exam and medical history including the following:
 - Avascular necrosis (AVN)
 - Osteoarthritis (OA)
 - Inflammatory arthritis (i.e. Rheumatoid arthritis)
 - Post-traumatic arthritis
- Patient has no history of previous prosthetic replacement device (any type, including surface replacement arthroplasty, endoprosthesis, etc.) of the affected hip joint(s).
- Patient has a Harris Hip Score <70 in the affected hip
- Patient is willing and able to provide written informed consent.
- Patient is willing and able to cooperate in the required post-operative therapy.
- Patient is willing and able to complete scheduled follow-up evaluations as described in the Informed Consent.
- Patient has participated in the Informed Consent process and has signed the Ethics Committee approved informed consent.

B. Exclusion Criteria

- The patient is:

- A prisoner
 - Mentally incompetent or unable to understand what participation in the study entails
 - A known alcohol or drug abuser
 - Anticipated to be non-compliant.
- The patient has a neuromuscular disorder, vascular disorder or other conditions that could contribute to prosthesis instability, prosthesis fixation failure, or complications in postoperative care.
- The patient has a vascular (large and small vessel disease) insufficiency.
- The patient has a neurologic condition in the ipsilateral or contralateral limb which affects lower limb function.
- The patient has a diagnosed systemic disease that could affect his/her safety or the study outcome.

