13.2 Variables for Analysis

Key demographic, baseline and peri-operative characteristics will be summarized for the *Allofit* IT Acetabular Shell with a *Longevity* Liner, both overall, and for each investigative site. Demographic, baseline, and peri-operative data will include:

- Demographics
- Age
- Gender
- Body Mass Index
- Alcohol use
- Tobacco use
- Baseline Characteristics
- Preoperative Harris Hip Pain Score
- Preoperative Harris Hip Functional Score
- Preoperative Activity Level
- Concomitant Medication
- Preoperative Radiographic assessment
- Diagnosis
- Oxford Patient Satisfaction
- Peri-Operative
- Surgery time
- Blood loss
- Hospital stay - defined as the date of discharge minus the date of surgery

Summaries will be done and compared preoperatively and at 6-12 weeks, 12 months, and 24 months initially. Long-term follow-up will be further compared at 3, 5, 7, and 10 years postoperatively.

For dichotomous variables and for variables with more than two responses, the number and percentage of patients in each category will be presented for the treatment. For continuous variables, descriptive statistics including counts, means, medians, standard deviations, minima, and maxima will be presented for the treatment group.

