13.3 Sample Size Justification

Sample size for the Allofit IT HXPE Study was estimated using the McHugh and Le method [43] with an alpha (Type I) error level of 0.05, a non-inferiority margin of 5.2% (δ), and an assumed survival rate of 90% at 10 years from ODEP.

The confidence limit approach, as discussed by McHugh and Le [43], can be used to calculate this sample size estimate. Specifically, we infer that the non-inferiority margin provides the absolute precision (5% δ) for the difference between the fixed rate in the historical control group and the rate estimated for the experimental group over the course of the study. Sample size estimation utilizes the following formula:

$$\delta\sqrt{n} = Z_{1-\alpha} \sqrt{\frac{p_{\text{exp}}(1-p_{\text{exp}})}{w_{\text{exp}}} + \frac{p_{\text{HC}}(1-p_{\text{HC}})}{w_{\text{HC}}}}$$

where δ represents the non-inferiority margin, n represents the group size, p_{exp} represents the rate in the experimental group, p_{HC} represents the rate in the historical control group, w_{exp} represents a weight (i.e., allocation weight) to accommodate unequal group size for the experimental group, w_{HC} represents the allocation weight to accommodate unequal group size for the historical control group, and $Z_{1-\alpha}$ represents the value of a standard normally distributed random variable corresponding to a cumulative probability of one minus alpha (0.05).

When adjusting for a ceiling in the calculation, and added attrition rate of 20% there is a sample size requirement of 195 for the experimental group. A sample size of 200 is therefore planned for enrolment in this study.

Sample size was estimated using SAS v. 9.1.3 for Windows.

14 Management of Incurrent Events

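### Apart from Kaplan-Meier survivorship of the device, the plan gives adverse device effect incidence neither a time-based method nor a denominator, and a percentage of all enrolled would modestly understate it over 10 years

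*Combined protocol and SAP*

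**What the plan says.** Section 13.1 (Analysis Objectives) sets the safety measure: "The assessment of safety will be evaluated by monitoring the frequency and incidence of adverse device effects in investigational subjects". Section 6 names the same kind of measure for adverse events, serious adverse events and serious adverse device effects. Neither section gives a denominator or a time scale.

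The next sentence of 13.1 adds: "As part of the safety profile, a survival analysis will be done". Section 6 supplies the endpoint and method for survivorship: "Based on removal or intended removal of the device and will be determined using the Kaplan-Meier method". No other endpoint is named for a survival analysis.

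For categorical variables in general, Section 13.2 says that "the number and percentage of patients in each category will be presented for the treatment". It does not say of which patients the percentage is taken. On timing it adds: "Long-term follow-up will be further compared at 3, 5, 7, and 10 years postoperatively".

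Three places show that follow-up will be unequal:
- Section 7.2: "the patient is expected to participate in the study for a time period of 10 years".
- Section 11.8: collection for a case stops when the subject completes the study, "is lost to follow-up, one or several devices are removed due to revision", or when the study closes.
- Section 13.3: the sample size includes an "added attrition rate of 20" per cent.

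In Appendix B, Form 12 (Adverse Event Report) records the date of onset. Form 14 (Study Completion) records the date of last assessment and any date of death.

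**The concern.** Form 12 has codes for dislocation, loosening, deep infection and other hip complications. Such an event can occur without removal of a component, and it is then outside the Kaplan-Meier analysis. For these events the plan leaves the counts and percentages of Section 13.2 as the only format on offer.

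A simple percentage is hard to read as an incidence when some patients are observed for 10 years and others for far less. If all enrolled patients form the denominator, someone lost in year 2 contributes as if observed without an event to year 10. The figure then falls short of the true incidence, in the direction that favours the device. If another denominator is used, the figure changes, and nothing in the plan prevents that choice from being made after the data are seen. Section 6 says the data serve the sponsor's vigilance and post-market surveillance duties, so the incidence figure should have one fixed meaning.

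**Working it through.** **Inputs.** From the documents: 10 years of follow-up (7.2), 20% attrition (13.3) and 200 enrolled (13.3). The plan states no adverse device effect rate, so there is no figure of its own to reproduce. Assumed: true 10-year incidence of 5%, 10% or 20%; loss unrelated to the risk of an event; and the event timings below.

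**Constant hazards, all enrolled as denominator.** Let l be the event hazard and m the attrition hazard. The crude proportion is l/(l+m) × [1 − exp(−10(l+m))].
- For a true 10%: l = −ln(0.90)/10 = 0.01054.
- For 20% attrition: m = −ln(0.80)/10 = 0.02231.
- Crude = 0.3207 × (1 − 0.90 × 0.80) = 0.3207 × 0.28 = 8.98%.

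The same formula gives 4.49% for a true 5% and 18.0% for a true 20%.

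**Other event timings.** In general, crude = ∫ G(t) dF(t) over 0 to 10 years. F is the true cumulative incidence, taken as Weibull. G is the share still followed, falling either exponentially or linearly to 80%. Each range below covers the two patterns of loss.

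| True 10-year incidence | Mostly early events (shape 0.3) | Constant hazard (shape 1) | Late events (shape 2) | Floor: all losses at once |
|---|---|---|---|---|
| 5% | 4.76-4.77% | 4.49-4.50% | 4.32-4.34% | 4.0% |
| 10% | 9.53-9.55% | 8.98-9.02% | 8.64-8.68% | 8.0% |
| 20% | 19.10-19.14% | 18.00-18.07% | 17.32-17.39% | 16.0% |

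The smallest relative understatement is 1 − 19.14/20 = 4.3%, the largest is 1 − 4.32/5 = 13.6%, and the floor is 20%. With 10% attrition the range is about 2-7%; with 40% it is about 9-28%.

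**Death as a competing event.** A cumulative incidence that treats death this way also keeps patients who died as never having had the event, so only non-death attrition produces a gap. Suppose half of the attrition hazard is death (an assumption), so the death hazard is 0.01116. For a net 10% the cumulative incidence is 0.01054/(0.01054 + 0.01116) × (1 − 0.90 × √0.80) = 0.4857 × 0.1950 = 9.47%. Against the crude 8.98%, the understatement is 0.49/9.47, or about 5%. If all attrition were death, the two would coincide.

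**Effect of the denominator.** With 200 enrolled, a true 10% and constant hazards, about 200 × 0.0898 = 18 patients have an observed event.
- Over all enrolled: 18/200 = 9.0%.
- Over the 200 × 0.80 = 160 not lost: 18/160 = 11.25%.
- Counting both events and patients only among those 160: 16/160 = 10%, but the events seen in patients later lost are discarded.

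Section 13.2 is compatible with any of the three.

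**Scale.** The 95% half-width for 10% with 200 patients is 1.96 × √(0.10 × 0.90/200) = 4.2 points. A one-point shift is about a quarter of that.

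**The case against.** Several stronger readings are tempting, and the documents do not support them.

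- **That safety is analysed with no allowance for follow-up time.** The sentence after the safety statement in 13.1 adds a survival analysis, and Section 6 specifies Kaplan-Meier for actual or intended removal. That endpoint is handled properly.
- **That 13.2 fixes adverse device effects as a percentage of patients.** The variables listed in 13.2 are demographic, baseline and peri-operative, and 13.1 speaks of frequency and incidence. Applying the general rule to adverse device effects is an inference, though no other format is offered.
- **That patients who leave early count as event-free.** Nothing says so. The summaries at successive time points could use patients followed to each point.
- **That an interim report would badly understate a 2-year incidence because enrolment is staggered over 24 months.** This assumes a percentage to date would be labelled as a 2-year incidence. Section 10.6 promises reports to investigators without timing or estimator, and the annual reports in 14.4.4 are mentioned only for explant summaries.

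It is also fair to say that the effect is small beside sampling error in an uncontrolled descriptive study. That stands, and it limits the weight of the point. It does not remove it: the bias does not shrink with more patients, and an undefined denominator is a gap in the plan whatever the size of the bias.

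**Conclusion.** The point holds as a gap in specification with a conditional bias. Device removal has a time-based analysis; other adverse device effects have neither a time-based method nor a denominator. If all enrolled patients are the denominator, 20% attrition over 10 years produces a relative understatement of about 4-14%, so that an assumed true 10% appears as about 8.6-9.5%. The understatement is lower to the extent that attrition is death handled as a competing event. The result rests on assumed event rates and timing, on loss unrelated to event risk, and on 20% attrition proving realistic. It is worth correcting, but it does not threaten the survivorship result.

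**What to change.** In Sections 13.1 and 13.2, state that adverse device effects and serious adverse device effects will be reported as cumulative incidence with 95% CI at 1, 2, 3, 5, 7 and 10 years. Measure time from surgery to the Form 12 onset date, censor at the last assessment on Form 14, and treat death as a competing event. State whether the unit is the patient or the hip, since bilateral cases carry two case IDs (10.3), and how a case whose data collection ends at revision is handled. Keep crude counts alongside, with their denominator named.

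The cost is SAP wording and a little more programming; no new data are needed. The reported incidences will be slightly less favourable than percentages of all enrolled. The method does not correct for loss that is itself related to hip problems, so the reasons for loss should be shown next to the estimates.
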